3.3.2 Follow-up for withdrawn subjects

The primary reason for participant study withdrawal would be due to early discharge from the Caron treatment program prior to successful completion. There would be no follow up with these patients.

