Diurnal cortisol: (Study Days 1,2,7,8) Saliva will be collected for cortisol measurement at 5-time points for two consecutive days at two different periods in the study, i.e. 8:00 AM before breakfast, 12:00 PM before lunch, 3:00 PM, 6:00 PM and 9:00 PM. The research staff will visit with the participant at approximately 3 PM (Day 0, 6, 9), 8 AM and 3 PM (Days 1, 2, 7, 8) to

provide fresh cortisol collection kits needed for the next collection and to collect provided saliva samples. Instructions on how to provide saliva samples will be given to the participant on Day 0. Specimens are collected using a cotton swab kit (Salivette, item #51.1534). It has been demonstrated that five samples are adequate to examine circadian variation of cortisol secretion. Cortisol levels will be determined using a commercially-available, high-sensitivity salivary cortisol enzyme immunoassay kit (Catalog # 11-CORHU-E01-SLV; Alpco, Salem, New Hampshire) designed to standardize the measurement of salivary cortisol across research and biomedical laboratories. Saliva cortisol assaying will be done by a certified lab technician in the research laboratory at the Penn State College of Medicine.

7.2.3 Abuse liability: Study Nights 1, 7, and the days following it (Study Days 2 and 8)

Abuse liability will be assessed with a modified protocol which includes the abuse liability battery morning, abuse liability battery night and the observer rated questionnaire. It is based on questions used in previous studies of abuse liability (17). The abuse liability –night battery will be completed by each research participant 30 min after medication administration on study Nights 1 and 7. The abuse liability battery – morning will be completed the morning after drug administration on study Day 2 and 8. The abuse liability battery- morning and night has the same questions related to drug liking, drug value questionnaire, drug effects questionnaire except that there are additional questions asking to categorize the medication effect to one of the seven classed of psychoactive substances on the abuse liability battery-night . The observer rated assessment will be completed by the medication nurse as described below. Our primary measures of abuse liability on the abuse liability battery- morning, night and the observer rated assessment will include the following 5 measures:

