7.2.4 Suvorexant: Study Nights 2-8

Patients will participate in an open 7-day trial of 20 mg suvorexant at night.

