19.2 Recording of Adverse Events

Subjects will be routinely questioned about adverse events from nursing staff at Caron during each nightly administration (all 9 nights of the study). Information will also be collected through the modified abuse liability assessment where patients will be given the Drug Effect questionnaire, administered 30 minutes after drug administration, and the next morning, to be used to evaluate how strong a drug effect was felt on a 5-item response scale, ranging from No Drug Effect to Very Strong Effect. This assessment will be administered in the evening of Study Night 1, as well as the morning of Study Day 2. Nursing staff will also complete an observer-rated questionnaire 30 minutes after drug administration on Study Night 1 and 7.

All adverse events should be reported immediately and will be addressed by the physician and other staff at Caron. The staff at Caron will then complete a Suvorexant Adverse Reaction Documentation form. All forms will be sent to and reviewed by the PI on our study team, [name]. In the event of a serious or life threatening adverse reaction, Caron medical staff will be immediately informed and address the situation. [name] will be contacted within 12 hours. Subjects are also encouraged to call the PI (with the assistance of the staff at Caron), [name] at [name] (cell) if they have questions, complaints or concerns about the research or believe they may have been harmed by being in the research study.

All adverse events (serious or non-serious) and abnormal test findings observed or reported to study team believed to be associated with the study drug(s) or device(s) will be followed until the event (or its sequela) or the abnormal test finding resolves or stabilizes at a level acceptable to the investigator.

An abnormal test finding will be classified as an adverse event if one or more of the following criteria are met:

• The test finding is accompanied by clinical symptoms

- The test finding necessitates additional diagnostic evaluation(s) or medical/surgical intervention; including significant additional concomitant drug treatment or other therapy
 NOTE: Simply repeating a test finding, in the absence of any of the other listed criteria, does not constitute an adverse event.
- The test finding leads to a change in study drug dosing or discontinuation of subject participation in the clinical research study
- The test finding is considered an adverse event by the investigator.

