19.7 Stopping Rules

In the event of an adverse reaction, the participant will consult with the nursing and doctoral staff at Caron to determine if they should continue with study. If deemed appropriate, participants will be removed from the study. If this event occurs, or the patient refuses to continue with the study, they will consult their doctors, and the medication will be properly destroyed, as described in section 7.4.6.4.

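### No adverse-event question is scheduled after a participant's last suvorexant dose, and 3.3.2 conflicts with 19.2 on following open events after early discharge

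*Combined protocol and SAP*

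**What the plan says.** **When AEs are asked about.** Section 19.2 has nursing staff question participants "during each nightly administration (all 9 nights of the study"). Table 2 in 7.2 numbers these nights 0 to 8. Nights 0 and 1 are on the participant's existing sleep medication, and suvorexant is given on Nights 2 to 8 (Table 2 and 7.2.4).

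**What happens on Day 9.** This is the day after the last dose. Table 1 lists the EMA diary and the modified ISI. The cortisol text in 7.2.2 adds a staff contact: "The research staff will visit with the participant at approximately 3 PM (Day 0, 6, 9"). It is described only for saliva kits and samples.

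**What happens to people who leave.**
- Section 3.3.2 states: "The primary reason for participant study withdrawal would be due to early discharge from the Caron treatment program prior to successful completion". The next sentence is "There would be no follow up with these patients".
- Section 3.3.1 says side effects are documented and reported to the FDA as required.
- Section 19.7 covers adverse reactions: "If deemed appropriate, participants will be removed from the study". Those participants, and those who refuse to go on, consult their doctors.
- Section 7.4.6.4 sends non-completers to their doctors about remaining sleep problems.

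**How long events are followed.** Section 19.2 says that AEs and abnormal test findings thought to be linked to the study drug or device "will be followed until the event (or its sequela) or the abnormal test finding resolves or stabilizes at a level acceptable to the investigator". It makes no exception for participants who have withdrawn.

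**The concern.** A question asked when a capsule is handed over mainly collects what happened since the previous capsule. If every scheduled question is tied to an administration, the last dose has no question after it. The effects listed in section 11 include complex sleep-related behaviour, amnesia, hallucinations and reduced alertness the next day. These would appear during the night or the following day, after that night's question has been asked.

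Section 8.3 promises a summary of adverse events, and 10.8 makes the report of a serious adverse event the ground for suspending the research. Both depend on events being found. People who leave because they feel unwell are the ones for whom a missing last question matters most.

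The second issue is a conflict of wording. One section says there is no follow-up after withdrawal, and another requires follow-up of certain events until they settle. Site staff could not tell from the text which applies to a participant who leaves with an event still open.

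**Working it through.** **1. The plan's own counts.** Nights 0 to 8 give 8 − 0 + 1 = 9 question nights, which matches the nine nights in 19.2. Nights 2 to 8 give 8 − 2 + 1 = 7 suvorexant doses, which matches the seven-night trial in 7.2.4 and 7.4.2.

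**2. Doses followed by a later scheduled question (completer).** Count a dose on Night d as followed if Night d + 1 is also a question night.
- Doses on Nights 2 to 7 are followed by the questions on Nights 3 to 8: 6 doses.
- The dose on Night 8 would need a Night 9 question, and there is none: 1 dose.
- Result: 6/7 = 85.7% followed, 1/7 = 14.3% not.

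**3. The same count for an early leaver.** A participant who takes k doses and leaves before the next administration has k − 1 of k doses followed: 0 of 1, 1 of 2, and so on to 5 of 6. The unfollowed dose is always the last one. Questioning before that point is intact.

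**4. Whether another scheduled item fills the gap.**
- *Abuse-liability battery and observer rating.* Section 7.2.3 puts these on Nights 1 and 7 and the mornings of Days 2 and 8, all before the Night 8 dose. Section 19.2 places the Drug Effect questionnaire on Night 1 and Day 2 only, which differs from 7.2.3 and should be aligned. On either version nothing follows Night 8.
- *Day 9 EMA.* The morning survey (7.2.2) records sleep quality, awakenings, daytime sleepiness and dreams with alcohol or drug content. It overlaps with some possible effects but is not an AE question.
- *Day 9 modified ISI and staff visit.* The first measures insomnia, and the second is described for saliva samples. Neither is given an AE item.
- *Other routes.* Section 10.3 relies on study procedures and on reports from staff and participants. Section 19.2 asks for immediate reporting and invites calls to the principal investigator. These are unscheduled.

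**5. Which drug each question reflects.** If the question is asked at or before dosing, those on Nights 0, 1 and 2 look back on the earlier sleep medication (3 of 9). Those on Nights 3 to 8 look back on suvorexant doses 1 to 6 (6 of 9). Section 8.3 gives no rule for assigning an event to one drug or the other.

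**6. Section 3.3.2 against 19.2.** There are two readings of the participants meant in 3.3.2.
- *Only those discharged early*, as the preceding sentence suggests. The conflict then arises for a participant discharged with an open event thought to be drug-related. Follow-up after other kinds of withdrawal is then not stated in 3.3.2.
- *All withdrawn subjects*, as the section heading suggests. The conflict then extends to anyone removed under 19.7 with such an event still open.

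On both readings at least one group falls under two incompatible statements.

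**7. Effect of one added question.** A question on Day 9 makes the completer's count 7 of 7. One at exit makes the leaver's count k of k.

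**The case against.** The strongest reply is that this is a small open-label pilot in a residential setting with nightly nurse contact, immediate AE reporting, a call line and a Day 9 visit, so little would be missed. That has weight: the consequence is a possible under-count, not a demonstrated one. It does not remove the gap, because none of these routes is a scheduled AE question after the final dose.

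Tables 1 and 2 have no AE row on any day, so the absence of one on Day 9 proves little. That is correct. The point rests on 19.2, which names the nightly administrations as the occasions for questioning.

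Section 19.2 says questioning takes place during administration and does not say whether before or after the capsule is swallowed. If afterwards, the Night 8 question might catch an immediate reaction, but still not an overnight or next-day one.

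Four stronger readings are tempting, and the documents do not support them:
- *Early leavers have no scheduled safety question at all.* They are asked at every administration until they leave.
- *Section 3.3.2 is all the protocol says about withdrawn subjects.* Sections 3.3.1, 7.4.6.4 and 19.7 also address them, although none schedules a study safety question after exit.
- *The conflict falls on precisely the patients who have events.* The duty in 19.2 covers only events believed to be linked to the drug or device. Someone removed for a reaction may stay in residence and may not be among those meant in 3.3.2.
- *Section 8.1 shows how many are affected.* It plans 36 participants and expects 25 evaluable data sets, but gives no reason for the difference and does not define evaluable. Missing actigraphy, cortisol or diary data could also make a data set non-evaluable, so this difference does not measure withdrawals.

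**Conclusion.** The point holds in two limited parts.

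First, as scheduled, the Night 8 dose is the one suvorexant dose of a completer's seven (14%) with no AE question after it. An early leaver's final dose has the same gap. The AE summary in 8.3 could therefore under-count overnight and next-day events after the last dose. This assumes that questioning is confined to the occasions 19.2 names and that a leaver goes before the next administration.

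Second, 3.3.2 and 19.2 contradict each other at least for a participant discharged early with an open drug-associated event, and for all withdrawn subjects if the heading of 3.3.2 governs. The number of such participants cannot be derived from the documents.

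The change is worth making because it costs little and concerns effects that the protocol itself lists as risks. It does not undermine the trial's design.

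**What to change.** 1. Add the AE question already used at nightly administration to the existing Day 9 staff visit, with the answer recorded on the existing adverse-reaction form.
2. Ask the same question once when a participant leaves early or is removed. The protocol describes no formal exit visit, so this assumes staff see the person at departure.
3. Reconcile 3.3.2 with 19.2. State which participants 3.3.2 refers to, and whether the absence of follow-up covers only study outcome assessments or also open events.
4. In 8.3, state that each AE will be classified by the last drug taken before onset (prior sleep medication or suvorexant), and record onset date and time so that this can be done.
5. Align 19.2 with 7.2.3 on when the Drug Effect questionnaire is given.

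If data collection has already finished, items 1 and 2 can no longer be applied. The report should then say that no AE question was scheduled after the final dose.

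The cost is one brief question at a contact with the participant, a short instruction to the staff who ask it, and a few sentences of text. No visit, dose or clinical rule changes.

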4.0 Recruitment Methods

4.1 Identification of subjects

Participants will be identified using two methods:

- The Caron based study coordinator will review the electronic medical records (EMR) of recently admitted patients and check for the inclusion/exclusion criteria
- Participants will also be identified through research flyers, which will be displayed in all units at the Caron Foundation. Interested patients will approach the Caron staff/counsellors who will in turn refer the subjects to the Caron based study coordinator. The Caron based study coordinator will check for inclusion/exclusion criteria by reviewing their EMR.

4.2 Recruitment process

Recruitment will use a two-step process:

- The Caron based study coordinator will complete a comprehensive REDCap screening and eligibility checklist to verify study eligibility based on established inclusion/exclusion criteria. It will be reviewed with the study coordinator at Hershey Medical Center (HMC) and the PI or his designee. If a Subject is deemed eligible to participate in the research based upon the preliminary assessment and if aggregable by the HMC coordinator and the PI of his designee, the Caron-based study coordinator will approach the participant to inquire about possible interest in the study. This study coordinator will review the study design, suvorexant information packet, and the inclusion/exclusion criteria with each prospective research participant.
- $\circ~$. Only subjects approved by the Hershey staff (study coordinator at Hershey Medical center and the PI or his designee) will be asked to review and sign an informed consent form if they wish to participate.

4.3 Recruitment materials

Flyers will be displayed on the treatment units at the Caron Foundation.

REDCap Screening Form (see the document "Screening Checklist" attached in CATS)

4.4 Eligibility/screening of subjects

In addition to the medical record review, participants may be asked questions designed to inform determination of eligibility from an additional screening script prior to signing the consent document .

5.0 Consent Process and Documentation

5.1 Consent Process

5.1.1 Obtaining Informed Consent

5.1.1.1 Timing and Location of Consent

Consent will be obtained on Day 0 (see study design) at the Caron Foundation by the Caron study coordinator after discussing the study in detail.

5.1.1.2 Coercion or Undue Influence during Consent

Subjects will be informed that participation is voluntary and that their decision to participate will not affect treatment at the Caron Foundation. The Caronbased study coordinator will comprehensively discuss the study with the patients, review consent documents, and answer all questions.

5.1.2 Waiver or alteration of the informed consent requirement

A waiver of consent is requested to review medical record information to determine preliminary eligibility to participate in the research.

5.2 Consent Documentation

5.2.1 Written Documentation of Consent

The consent process will be documented in writing with the long form of consent documentation:

- The current IRB approved consent form will be obtained.
- We will verify that we are using the most current IRB-approved version of the study specific consent form and that the consent form is in language understandable to the subject.
- A copy of the consent form will be provided to the subject. Whenever possible the consent form will be provided to the subject in advance of discussion.

5.2.2 Waiver of Documentation of Consent (Implied consent, Verbal consent, etc.)

The study team intends to potentially ask subjects eligibility questions prior to written consent. The study team will obtain verbal consent from the participant to ask questions detailed in the additional screening script.

5.3 Consent – Other Considerations

5.3.1 Non-English Speaking Subjects

Not applicable.

5.3.2 Cognitively Impaired Adults

5.3.2.1 Capability of Providing Consent

Not applicable.

5.3.2.2 Adults Unable To Consent

Not applicable.

5.3.2.3 Assent of Adults Unable to Consent

Not applicable.

5.3.3 Subjects who are not yet adults (infants, children, teenagers)

5.3.3.1 Parental Permission

Not applicable.

5.3.3.2 Assent of subjects who are not yet adults

Not applicable.

6.0 HIPAA Research Authorization and/or Waiver or Alteration of Authorization

6.1 Authorization and/or Waiver or Alteration of Authorization for the Uses and Disclosures of PHI

Check all that apply:

- Not applicable, no identifiable protected health information (PHI) is accessed, used or disclosed in this study. [Mark all parts of sections 6.2 and 6.3 as not applicable]
- Authorization will be obtained and documented as part of the consent process. [If this is the only box checked, mark sections 6.2 and 6.3 as not applicable]
- Partial waiver is requested for recruitment purposes only (Check this box if patients' medical records will be accessed to determine eligibility before consent/authorization has been obtained). [Complete all parts of sections 6.2 and 6.3]
- **Full waiver is requested for entire research study (e.g., medical record review studies).** [Complete all parts of sections 6.2 and 6.3]
- Alteration is requested to waive requirement for written documentation of authorization (verbal authorization will be obtained). [Complete all parts of sections 6.2 and 6.3]
- 6.2 Waiver or Alteration of Authorization for the Uses and Disclosures of PHI
 - 6.2.1 Access, use or disclosure of PHI representing no more than a minimal risk to the privacy of the individual
 - **6.2.1.1 Plan to protect PHI from improper use or disclosure** Information is included in the "Confidentiality, Privacy and Data Management" section of this protocol.

6.2.1.2 Plan to destroy identifiers or a justification for retaining identifiers

Upon study completion, all electronic patient research information will be deleted from all research sources. Any hard copy patient information collected for research will be placed in one of HMC's patient information bins to be shredded in compliance with HIPAA regulations and PSU research document retention policies.

6.2.2 Explanation for why the research could not practicably be conducted without access to and use of PHI

Information must be obtained from the subject's electronic medical record at Caron during recruitment to determine eligibility and, in some cases, to confirm information discussed with the subject in regard to their medical history.

6.2.3 Explanation for why the research could not practicably be conducted without the waiver or alteration of authorization

The waiver is requested only for recruitment to determine subject eligibility to ensure that no medical conditions that fall into the exclusion criteria are present and would thus preclude enrollment. This waiver will minimize the enrollment of subjects' who may ultimately fail to meet the study inclusion/exclusion criteria.

6.3 Waiver or alteration of authorization statements of agreement

Protected health information obtained as part of this research will not be reused or disclosed to any other person or entity, except as required by law, for authorized oversight of the research study, or for other permitted uses and disclosures according to federal regulations.

The research team will collect only information essential to the study and in accord with the 'Minimum Necessary' standard (information reasonably necessary to accomplish the objectives of the research) per federal regulations.

Access to the information will be limited, to the greatest extent possible, within the research team. All disclosures or releases of identifiable information granted under this waiver will be accounted for and documented.

7.0 Study Design and Procedures

7.1 Study Design

Open label, pilot observational study of suvorexant, an orexin 1 / 2 receptor antagonist, for the treatment of sleep disturbance in patients in residential treatment for opioid or alcohol use disorder.

7.2 Study Procedures

When a medication is studied for a new indication, or in a new population, it is common (in clinical neuropsychopharmacology) to conduct the first study in an open trial. We plan to study two groups of patients in an open 7-day trial of 20 mg suvorexant HS, following a two-day baseline during which patients will be taking a previously prescribed sleep medication (i.e. trazodone, mirtazapine, or melatonin) before switching to suvorexant. The study design includes a combination of assessments, and the collection of biological samples. Participants will be enrolled in the study for a total of 10 days (9 nights). Table 1 references the daytime questionnaires and procedures, and Table 2 represents the night questionnaires and procedures. Night is considered to be the time after the patient takes the medication. In our study, the night falls after the day.

Table 1. Daytime questionnaires and procedures.

Study Day	0	1	2	3	4	5	6	7	8	9
Consent and										
Screening (Form										
90 AI/DI, MINI	X									
Screen/MINI 7.0.2,										
HAM-D)										
EMA		X	X	X	X	X	Χ	X	X	Χ
Modified ISI	Χ									Χ
Modified PSQI	Χ									
DNA Collection*	Χ									
Cortisol Collection		X	X					X	X	
Abuse Liability			X						X	
Battery – Morning			Δ						Λ	

Table 2. Night questionnaires and procedures.

Study Night	0	1	2	3	4	5	6	7	8
Suvorexant			1	2	3	4	5	6	7
Baseline**	X	X							
Suvorexant Administration			X	X	X	X	X	X	X
Actigraphy/Logs	Χ	X	X	X	X	X	X	X	X
Abuse Liability Battery - Night		X						X	
Observer Rated Questionnaire		X						X	

*Optional saliva for patients with opioid use disorder only

**Current medicine regime including antidepressants/melatonin

Abbreviations: EMA, ecological momentary assessment; ISI, Insomnia Severity Index; PSQI, Pittsburgh Sleep Quality Index.

7.2.1 Consent and Screening: Study Day 0

After signing the informed consent document, the Caron based study coordinator will complete a comprehensive screening assessment with each participant to further evaluate their eligibility in the study. The comprehensive screening assessment includes questionnaires to evaluate psychiatric comorbidities, sleep quality, depression and previous drug/alcohol use. The screening assessment questionnaires will be administered to the patients by the Caron based study coordinator on paper/ electronic tablet using the REDCap software. The screening questionnaires will include:

• The M.I.N.I International Neuropsychiatric Interview (M.I.N.I. 7.0.2; if applicable) (10) which provides psychiatric diagnosis.

• The Hamilton Depression Rating Scale (HAM-D; 11) will be used to provide a continuous measure of depressive symptomatology and severity.

• The Form 90-AI or Form 90-DI (12) will be administered to assess recent and lifetime history of drug and alcohol use, respectively. Recent substance use will document the 90 days prior to residential treatment admittance.

- The Pittsburgh Sleep Quality Index (PSQI; modified) (13) will be used to document the subjective severity of sleep complaints.
- The Insomnia Severity Index (ISI; modified) (14) will measure insomnia related symptoms. This assessment will also be administered on Study Day 9.

The study coordinator at Caron will also provide the patient with an actigraph, sleep log and EMA smartphone which the patient will return after completing the study.

Optional Research: Participants who are being treated for opiate dependence will be asked if they would like to give a DNA sample from saliva using an Oragene collection kit to be used for DNA extraction. This is not mandatory. The samples will be stored at Department of Psychiatry, Penn State Hershey Medical center until the end of the study. When the study is complete, the samples will be shipped to [name] at University Park who will process the data for genotyping. He will purify the DNA from the saliva in his laboratory. Genotypes will be established from approximately 5 million sites in the genome. Candidates for single genes to study include the opioid receptor genes and the alcohol dehydrogenase genes. He will include these new genes in the analyses of the relation between suvorexant and opioid use. In addition to testing for genotype (the bases present in DNA), he will test for patterns of DNA methylation, which is an underpinning of epigenetics.

